9.1.5 Noncutaneous progression

Progressive disease includes new visceral sites of involvement or progression of visceral disease or the development of new or increasing tumor-associated edema or effusion lasting at least 1 week, which interferes with the participant’s normal activities. Progressive visceral disease, for measurable and evaluable disease, should be analogous to non-KS response criteria.

9.1.6 Recurrent disease

Recurrent disease is defined as the appearance of tumor following documentation of a complete remission.

9.1.7 Time to response

Time to response is defined as time from the first dose of chemotherapy until

documentation of first response.

9.1.8 Time to progression

Time to progression is defined as time from initiation of chemotherapy to documentation of first progression.

9.1.9 Response duration

Response duration is defined as the time from first documentation of response to documentation of first progression.

10.0 STATISTICAL CONSIDERATIONS

10.1 Study Design/Endpoints

Currently approved cytotoxic chemotherapy regimens result in a roughly 40% partial or complete response (total response) rate in persons who are not ART-naïve (who initiate ART and chemotherapy concurrently). Our hypothesis is that the dose-escalation regimen will result in at least a 20% improvement in PR or CR above the historically defined rate of spontaneous KS regression, which is 20%. We chose to evaluate a 20% improvement in total response rate because we felt that this would be both a clinically significant improvement and at least equivalent to current chemotherapy. Because NFV has many fewer toxicities and requires less monitoring, oral administration, and less cost and potential for better access compared to chemotherapy, a finding of at least equivalence could be considered an improvement over the standard-of-care. Because the cost and feasibility of using an all-oral NFV regimen in resource-limited settings would provide a significant implementation and access benefit over cytotoxic chemotherapy, we feel strongly that NFV should be proven similarly efficacious to current chemotherapy, rather than superior to it. Therefore, we have chosen a design with 90% power at a one-sided 10% significance level to test the hypothesis that 40% of participants receiving NFV at standard followed by high-dosing regimens will be able to attain PR or CR. The null hypothesis is that we will fail to detect a response superior to the rate of spontaneous tumor regression (20%). Participants from both the international and domestic protocol will contribute to the single analysis plan, which is based on HIV status and not site of recruitment.

Primary objective

To determine the efficacy of a therapeutic escalation strategy consisting of standard dose nelfinavir, followed by high dose nelfinavir, for the treatment of Kaposi sarcoma (KS) tumor lesions. The binomial proportion and its exact 95% confidence interval will be used to estimate the response rate in the study. With 36 evaluable participants, the null hypothesis will be rejected if 11 or more participants respond. Response rates will be estimated using the binomial proportion and its exact 95% confidence interval separately for HIV positive and HIV negative participants.

Secondary objectives

- To evaluate the safety of high dose nelfinavir among participants with KS.

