Proposals to evaluate the effects of nelfinavir on KSHV infection and KS in HIV-infected individuals have focused on the potential confounding by the antiretroviral activity of nelfinavir; even with adjustment for HIV viral load and CD4 counts, any effect of nelfinavir might still be due to enhanced control of HIV infection. By including participants with KS but without HIV, we have the ability to definitively examine the direct clinical antitumor and antiviral effects of nelfinavir, which may provide valuable clinical information regarding the treatment of KS in HIV-negative individuals, as well as those who are HIV-infected. Additionally, because all prior studies in reducing incident KS or treating KS with PIs have focused on ART-naïve persons, it is difficult to compare studies of persons receiving modern highly-active ART regimens, that do or do not include PIs, directly for their effects on KS and KSHV, because it is known that PIs provide more rapid virologic and immunologic responses than triple nucleoside/nucleotide reverse transcriptase inhibitor (NRTI) regimens or non-nucleoside reverse transcriptase inhibitor (NNRTI) regimens (unclear vs. recently utilized integrase inhibitors). Therefore, in this study, we propose to add nelfinavir to stable complete ART regimens in HIV-infected persons and in HIV-negative KS participants, in order to remove the HIV virologic and immunologic confounding implied in PI use. This is distinct from modern trials, which evaluate cytotoxic chemotherapy plus ART-initiation in previously ART-naïve persons. Thus, we expect we

may see less robust responses in persons with stable disease (SD) despite ongoing ART usage⁵⁸⁻⁶⁰. Comparable trials of novel agents, such as valproic acid or VEGF inhibitors in persons already on stable ART at enrollment, showed much smaller effect sizes between 20-30%⁶¹⁻⁶⁴.

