The proposed trial is based on the hypothesis that nelfinavir might be repurposed as an anticancer agent, and that among all cancers that might be targeted, the effects of nelfinavir on Akt signaling, angiogenesis pathways, viral gene expression, and infectious virion production seem almost tailored to the treatment of KS. And, save for (likely undue) concerns about diarrhea, the side effect profile is gentler than for any of the approved treatments (paclitaxel, liposomal doxorubicin) or those presently being investigated by the AMC (bortezomib, lenalidomide). Therefore, we propose to evaluate a treatment strategy of nelfinavir in AIDS-associated and in HIV-negative KS participants to determine tumor response and virologic suppression. The strategy starts with standard dose (1250 mg BID) nelfinavir to determine whether KS patients may demonstrate a tumor response and to determine the antiviral activity of the FDA-approved regimen. Those participants with tumor progression or no response to standard dose nelfinavir will receive high dose (3125 mg BID) nelfinavir therapy, which has been found to be well tolerated in clinical trials of cancer patients. In addition to tumor and virologic outcomes, these participants will be assessed for the possibility of bone marrow suppression and other toxicities that can occur with nelfinavir, especially in combination with a full ART regimen.

Clinical tumor responses would pave the way for further evaluation of nelfinavir alone as an antitumor agent. Given the possibility of activation of viral lytic gene expression, evaluation of the combination of nelfinavir with an agent such as ganciclovir or fialuridine (FIAU) that would kill infected cells might be pursued. This study will evaluate the safety and efficacy of nelfinavir to treat KS. Furthermore, findings regarding the tumor and virologic response in participants may provide valuable insights into KS pathogenesis and the mechanism(s) of action of nelfinavir, which may translate into knowledge to guide therapy of KS worldwide. Finally, if nelfinavir was found to have an antiviral effect on KSHV *in vivo*, the drug may play a role in strategies to prevent the development of KS among persons deemed to be at high risk.

High-Dose Safety Review

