10.2 Sample Size/Accrual Rate

The study is designed to test the null hypothesis that the response rate is less than or equal to 20% against the alternative that it is 40% or greater with 90% power at a one-sided 10% significance level which will require a sample size of 36 evaluable participants using the exact test for a single proportion^{3,4}.

The plan is to enroll 18 participants who are HIV-positive and 18 who are HIV-negative, at an estimated accrual rate of 1-2 participants/month. Participants from both the international and domestic sites will contribute to the single analysis plan, which is based on HIV status and not site of recruitment.

Evaluable participants for all endpoints are defined as participants who meet all the eligibility criteria, enroll on the study, and receive at least one dose of treatment. Participants who enroll but are not treated will be replaced.

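### Section 10.1 says the design should prove nelfinavir similar to chemotherapy (roughly 40%), but the only primary test is against 20% and is met at 11 of 36 (30.6%)

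*Combined protocol and SAP*

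**What the plan says.** Section 10.1 opens with the benchmark: "Currently approved cytotoxic chemotherapy regimens result in a roughly 40% partial or complete response (total response) rate". It sets spontaneous regression at 20% and aims for a 20-point improvement on that, partly because the result would then be at least equivalent to chemotherapy. It adds that finding at least equivalence could count as an improvement on standard of care, given lower toxicity, cost and monitoring. It then says "we feel strongly that NFV should be proven similarly efficacious to current chemotherapy, rather than superior to it", and the next sentence presents the design as following from this: "Therefore, we have chosen a design with 90% power at a one-sided 10% significance level to test the hypothesis that 40% of participants" will reach partial or complete response.

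The hypothesis actually tested is different in kind. In 10.1 the null is the 20% rate of spontaneous regression. Section 10.2 repeats it: "The study is designed to test the null hypothesis that the response rate is less than or equal to 20" per cent, with 40% or more as the alternative. The decision rule in 10.1 is "With 36 evaluable participants, the null hypothesis will be rejected if 11 or more participants respond". The rest of the primary analysis is estimation, with exact 95% confidence intervals overall and by HIV status. Neither section states an equivalence or non-inferiority hypothesis, a margin against 40%, or a chemotherapy arm.

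**The concern.** The two halves of the paragraph do not match. The reason given is proof of similarity to a treatment with a rate near 40%. The test that follows can only show that the rate is above 20%. The 40% enters only as the value at which power is calculated, and rejecting 20% does not establish a rate near 40%.

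What is at stake is the claim that a positive result may carry. Eleven responders would meet the primary criterion. A report could then cite 10.1 in support of saying that nelfinavir had been shown to be similar to chemotherapy, although nothing in the design tests that.

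**Working it through.** **Inputs.** Null rate 20%, alternative 40%, one-sided alpha 10%, power 90% and n = 36 (10.1 and 10.2); cut-off 11 and exact 95% CI (10.1); chemotherapy rate roughly 40% (10.1).

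**Step 1: reproduce the design.** With X ~ Binomial(36, p),

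P(X ≥ 11 | p) = Σ C(36, k) p^k (1 − p)^(36 − k), summed over k = 11 to 36.

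- At p = 0.20: 0.0889, within the 0.10 limit. A cut-off of 10 would give 0.168, so 11 is the smallest admissible cut-off.
- At p = 0.40: 0.9096, above the 0.90 required.
- With n = 35 and its cut-off of 11, power is 0.888. In a search from n = 15 upwards, 36 is the first n to meet both limits.

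The plan's figures are correct.

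**Step 2: how often is the rule met at rates between 20% and 40%?** The same formula gives:

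| True response rate | P(11 or more of 36) |
|---|---|
| 20% | 0.089 |
| 25% | 0.27 |
| 30% | 0.53 |
| 35% | 0.77 |
| 40% | 0.91 |

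A treatment 10 points below the chemotherapy figure passes about half the time, and one 5 points below passes about three times in four.

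**Step 3: what does the planned interval show?** The exact (Clopper-Pearson) 95% limits for x responders are the 0.025 quantile of Beta(x, 37 − x) and the 0.975 quantile of Beta(x + 1, 36 − x).

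| Responders | Observed rate | Exact 95% CI |
|---|---|---|
| 11/36 | 30.6% | 16.3% to 48.1% |
| 14/36 | 38.9% | 23.1% to 56.5% |
| 15/36 | 41.7% | 25.5% to 59.2% |
| 17/36 | 47.2% | 30.4% to 64.5% |

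At the cut-off the observed rate is 40 − 30.6 = 9.4 points below 40%. With 15 responders, just above 40% observed, the lower limit is still 40 − 25.5 = 14.5 points below 40%. A true rate of 30% is excluded from 17/36 by the planned two-sided 95% CI. At the trial's own one-sided 10% level it is excluded from 15/36, since P(X ≥ 15 | 0.30) = 0.092.

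**Step 4: the rule read as a comparison with 40%.** Treat 40% as fixed and test a rate of 40% minus a margin, one-sided at 10%. The present rule is then a non-inferiority test with a margin of 40 − 20 = 20 points, the whole difference between chemotherapy and spontaneous regression. The documents state no margin. If one of 10 points is assumed for illustration, 15 of 36 would be needed and power at a true 40% would be 0.48. With 5 points, 17 of 36 would be needed and power would be 0.24.

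**The case against.** The strongest reply is that the sentence is motivation, not a hypothesis. The remark about not needing superiority explains why the alternative is 40% and no higher. The formal statements are sound: the primary objective is only to determine efficacy, the null of 20% appears in both 10.1 and 10.2, and an analyst who follows them cannot run the wrong test. This is a pilot, the 95% CI will be reported, and section 2.3 names the next step modestly: "Clinical tumor responses would pave the way for further evaluation of nelfinavir alone as an antitumor agent".

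Most of that stands, and it limits the harm. It does not rescue the word for proof, or the sentence that makes the design its consequence. Nothing else in 10.1 limits the conclusion, and the remark about a finding of at least equivalence points the same way. The interval is only a partial safeguard: at 11/36 it contains both 20% and 40%, so a reader could cite the 40% as support.

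Stronger readings are tempting but not supported:

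- *That the trial formally sets out to show equivalence, or is wrongly sized.* No objective, hypothesis or decision rule claims equivalence, and 36 with a cut-off of 11 is right for the test that is stated. The margins in the working are assumptions, not requirements of the plan.
- *That section 2.3 shows nelfinavir is likely to fall short of 40%.* It says comparable agents "in persons already on stable ART at enrollment, showed much smaller effect sizes between 20-30" per cent, but does not say that these are response rates, and it concerns only people on stable ART. Half the planned enrolment is HIV-negative. The point does not rest on that remark.

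**Conclusion.** The concern holds as a fault in the stated rationale. Section 10.1 attributes to the design a property it does not have: a positive primary result supports a response rate above 20%, not similarity to a rate near 40%. The size of the gap is given by the chance of a positive result at true rates short of 40%: 0.53 at 30% and 0.77 at 35%. These figures assume 36 evaluable participants, independent responses with a common rate, and the 40% benchmark taken as the plan states it, without uncertainty. The correction is worth making before results are known because it settles what a positive result may be said to show. It is a correction of wording and of the permitted conclusion only.

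**What to change.** In 10.1, keep the explanation that 40% was chosen because it matches the reported chemotherapy rate. Replace only the clause "we feel strongly that NFV should be proven similarly efficacious to current chemotherapy, rather than superior to it" with:

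> the target response rate was set close to that reported for current chemotherapy, rather than above it

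Then add:

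> Eleven or more responses among 36 evaluable participants support only the conclusion that the response rate exceeds 20%; the study does not test equivalence or similarity to chemotherapy.

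This costs one replaced clause and one added sentence. The downside is that the claim available after a positive result is less favourable.

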- K8.1 will be measured by immunohistochemistry. A study participant's K8.1 expression will be considered to have increased with treatment if the percentage of cells with K8.1 staining is at least 20% and has increased at least 50% from baseline measures. With 36 study participants, the null hypothesis that the proportion of study participants who demonstrate an increase is 1% and can be tested against the alternative that it is 20% or greater at the one-sided significance level of 0.10 with power of 0.92 using the exact test for a single proportion (REF: Chernick MR, Liu CY: The saw-toothed behavior of power versus sample size and software solutions: single binomial proportion using exact methods. *The American Statistician* 56: 149-155, 2002.) Thus, the proportion of study participants who demonstrate an increase in K8.1 expression will be estimated using the binomial proportion and its exact 95% confidence interval.

Exploratory objectives

- To assess the effect of nelfinavir on KSHV and EBV copy number in PBMC and plasma.
- To assess the effect of nelfinavir on HSV, CMV, and EBV in saliva.
- KSHV detection in plasma (viremia) and oral shedding will be calculated at baseline and on NFV treatment. An analysis will also be performed for shedding of HSV, CMV, and EBV. Kaplan-Meier curves will also be created to demonstrate percent of participants demonstrating the presence of each of the above viruses in blood and saliva as a function of time and stage of treatment. For each herpesvirus and source of samples (oral or plasma), the following analyses will be done:
 - McNemar's chi-square test will be used to evaluate the detection of the herpesvirus prior to treatment and during treatment.
 - Generalized estimating equations (GEE) using a binomial distribution will be used to evaluate the detection of KSHV in plasma and oral specimens over time. Log10 transformations will be applied to the viral load data, and the median log viral load will be estimated for each participant prior to treatment and at time points post treatment. Generalized estimating equations (GEE) will be used to assess change over time with

respect to these measures.

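### The power of 0.92 stated for the K8.1 exact test does not follow from its own inputs, which give 0.997

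*Combined protocol and SAP*

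**What the plan says.** The last item under the secondary objectives in Section 10.1 of the combined protocol and SAP treats K8.1 staining as a yes/no outcome for each participant. The null hypothesis is that "the proportion of study participants who demonstrate an increase is 1% and can be tested against the alternative that it is 20% or greater". The calculation is for 36 participants, and the operating characteristics are given as "at the one-sided significance level of 0.10 with power of 0.92 using the exact test for a single proportion". No rejection cutoff is printed, and no smaller number of usable biopsy pairs is mentioned. The item closes by saying that "the proportion of study participants who demonstrate an increase in K8.1 expression will be estimated using the binomial proportion", with an exact 95% confidence interval.

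The primary endpoint is handled by the same kind of test in the same section, but with its cutoff stated: "With 36 evaluable participants, the null hypothesis will be rejected if 11 or more participants respond". Section 10.2 derives the trial size from that endpoint, "which will require a sample size of 36 evaluable participants".

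**The concern.** For an exact one-sample binomial test, the sample size, null rate, alternative rate and one-sided significance level determine the cutoff, the true size and the power. There is nothing left to choose. A 1% null against a 20% alternative is a very wide gap for 36 participants, so 0.92 looks too low.

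If the figure does not follow from the inputs, a reader cannot tell whether the power or one of the inputs is in error. If the inputs are right, the test is stronger than claimed and the error is harmless in direction. If 0.92 is right, then the alternative or the number of participants is misprinted, and the plan misdescribes what the K8.1 analysis can detect.

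**Working it through.** **Inputs, all from the K8.1 item in Section 10.1:** n = 36, p0 = 0.01, p1 = 0.20, one-sided alpha = 0.10, exact test for one proportion. Stated power: 0.92.

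**Check of the method on the primary endpoint.** With n = 36, 20% against 40% and one-sided 10%:

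- P(X ≥ 10 | 0.20) = 0.1676, which is too large.
- P(X ≥ 11 | 0.20) = 0.0889, so the cutoff is 11, as the plan says.
- P(X ≥ 11 | 0.40) = 0.9096, which agrees with the stated 90%.

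The exact binomial calculation reproduces the plan's primary rule.

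**Cutoff for K8.1.** Take the smallest r with P(X ≥ r | 36, 0.01) ≤ 0.10.

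- P(X ≥ 1) = 1 − 0.99^36 = 0.3036, which is too large.
- P(X ≥ 2) = 1 − 0.99^36 − 36 × 0.01 × 0.99^35 = 0.0503, which is acceptable.

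The cutoff is 2 or more of 36, with exact size 0.050.

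**Power at 20%.** P(X ≥ 2 | 36, 0.20) = 1 − 0.8^36 − 36 × 0.2 × 0.8^35 = 1 − 0.0003 − 0.0029 = **0.9968**. Since 20% is the least favourable point of the alternative, power at higher rates is greater still.

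**Can 0.92 be reached by changing one input?** The null rate and alpha act only through the cutoff:

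| Cutoff | Size at 1% | Power at 20% |
|---|---|---|
| ≥ 2 | 0.0503 | 0.9968 |
| ≥ 3 | 0.0056 | 0.9840 |
| ≥ 4 | 0.0005 | 0.9478 |
| ≥ 5 | 0.00003 | 0.8731 |

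Power falls from 0.948 to 0.873 with nothing between.

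- *Alpha only:* 0.05, 0.025 or 0.01 gives cutoff 3 (0.984); 0.005 gives cutoff 4 (0.948).
- *Null only:* 2% or 3% gives cutoff 3 (0.984); 4% gives cutoff 4 (0.948); 5% gives cutoff 5 (0.873).
- *Number of participants only:* the cutoff is 2 for every n from 11 to 53. Power is 0.9968 at 36, 0.9895 at 30, 0.9726 at 25, 0.9308 at 20, 0.9171 at 19 and 0.9009 at 18. Below 11 the cutoff is 1, and power is at most 0.8926 (n = 10). Of all sizes from 8 to 36, only 19 rounds to 0.92.
- *Alternative only:* 11% with cutoff 2 gives 0.918. An alternative of 15% gives 0.922, but only with cutoff 3, which is not the one-sided 0.10 cutoff for a 1% null, so a second input would also have to change.

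**Approximations at the stated inputs.** The standard error is √(0.01 × 0.99/36) = 0.0166 under the null and √(0.20 × 0.80/36) = 0.0667 under the alternative.

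- Normal, both variances: Φ[(0.19 − 1.2816 × 0.0166)/0.0667] = 0.994.
- Normal, alternative variance only: Φ[0.19/0.0667 − 1.2816] = 0.942.
- The same with a continuity correction of 1/72: Φ[0.1761/0.0667 − 1.2816] = 0.913.
- Arcsine: 0.999.

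None rounds to 0.92, and the plan names the exact test.

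**The case against.** The best defence is that 0.92 quietly allows for missing tissue. K8.1 change needs a baseline and an on-treatment biopsy. The high-dose biopsy in Section 8.2.8.2 exists only for participants who escalate, and Section 8.1.12.2 foresees baseline tissue that is inadequate for immunohistochemistry. With 19 usable pairs and the same cutoff, power is 0.917. That is a possible origin of the figure, but it does not rescue the text. It means losing 17 of 36, the sentence itself says 36 participants, and Section 10.2 defines evaluability for all endpoints by eligibility, enrolment and one dose. Any smaller loss, down to 20 pairs, leaves power at 0.931 or more. If 19 pairs was meant, the number is misreported and needs correcting.

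A second objection is that the plan presents K8.1 as estimation and sets no cutoff, so printing one adds a decision rule. There is something in this. However, the cutoff is already implied by the stated inputs, and it can be given as the basis of the power figure without changing how the result is reported.

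A third is that the consequence is slight. That stands, and it is why the point is minor.

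**Conclusion.** The stated power is wrong as written. On the plan's own inputs the exact test rejects at 2 or more of 36 and has power 0.997, which is 0.077 above the printed 0.92. The result assumes that each of the 36 participants contributes one independent yes/no outcome, as the sentence implies.

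Which number is at fault cannot be settled from the documents. The null rate and the significance level can be ruled out as the sole cause; the power figure, the alternative and the number of participants cannot. If the inputs are right, the error is conservative. The trial size of 36, the primary rule and the reporting of K8.1 as a proportion with its interval are unaffected.

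**What to change.** Change one sentence in Section 10.1, after checking the original calculation.

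- If the inputs are as intended, replace 0.92 with 0.997 and show its basis, for example: *the null is rejected if 2 or more of 36 participants show an increase; exact size 0.050, power 0.997 at a true rate of 20%*.
- If an input was misreported, such as the alternative or the number of evaluable biopsy pairs, correct it and give the cutoff, exact size and power that go with it.

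The cost is the edit itself. Biopsies, staining, sample size and planned analyses stay as they are.

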PBMC/Plasma viremia: Because KSHV can reactivate sporadically, and viremia is not always persistent in persons with KS (present on median of 20% of days in endemic KS and on 67% of days in HIV-associated KS in Uganda¹ the more

samples obtained, the more stability and precision in estimates. Therefore, we would like to obtain 2 samples pre-treatment and 8 samples on treatment. The timing of those samples is not important in a Poisson mixed effects model, so we are basing the timing on feasibility. For example, 2 samples can be achieved through weekly sampling during the 4 weeks pre-treatment. Eight samples on treatment can be obtained twice monthly in order to coordinate the blood draw schedule with clinical/tumor assessment visits and safety lab blood draws, which will also occur on this schedule (safety labs monthly but coordinated with bi-weekly visits); this will reduce burden on participant and maximize study resources. Effect of the study drug on KSHV replication is an important outcome of this study.

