APPENDIX II: BIOMARKERS AND CORRELATIVE STUDIES

Sample	Collected in	Baseline/Screening Weeks -4 to 0	Treatment start/ Day 0	SD-NFV ¹	HD-NFV ¹	Special Handling	Where to Send
3mm skin biopsies for immunohistochemistry expression of LANA and 3 lytic gene products; KSHV gene expression arrays	1 biopsy in formalin (for IHC); 1 biopsy in RNAlater (for gene expression)	Weeks -4 to 0, once	--	2 weeks after starting SD-NFV	2 weeks after starting HD-NFV	See Appendix X	See Appendix X
Whole blood for separation into plasma and PBMCs for KSHV and EBV qPCR	One 8.5 ml ACD (yellow top) tube	2 total blood samples during weeks -4 to 0	--	--	Each visit (every 2 weeks) after starting HD-NFV (8 samples total)	See Appendix X	See Appendix X
Oral swabs for KSHV, EBV, CMV, and HSV	Study-specific swabs/tubes	14 total daily swabs, collected during weeks -4 to 0	--	--	2 swabs per week while on HD-NFV for a total of 14 swabs	Stored at room temperature. Ship in batches bi-weekly (Sun-Wed);	See Appendix X
Genotyping	To be performed using DNA from PBMC	Once	--	--	--	See Appendix X	See Appendix X
Peripheral blood for PK	~6 ml of whole blood processed as plasma (one 6 ml potassium EDTA lavender top tube)	--	Immediately (- 3 days) pre-dose at each visit (every 2 weeks) starting on Week 1/cycle 1 through the completion of Week 15/cycle 9 (9 total samples)			Stored on ice, plasma separated within 30 minutes and frozen at ~ -70. Ship in batches (Mon-Wed)	See Appendix IX

1. Study weeks and timing of SD-NFV and HD-NFV may vary based on response; see [Section 4.1](#). Scheduled study visits will be every 2 weeks.

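### A per-participant median log viral load is a poor summary for intermittently detected virus with unequal sample counts: pooled it can fake a fall in blood, by time point a rise in saliva

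*Combined protocol and SAP*

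**What the plan says.** The viral-load analysis is the last item under the exploratory objectives in Section 10.1.

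- **Scope:** "For each herpesvirus and source of samples (oral or plasma), the following analyses will be done".
- **Scale:** "Log10 transformations will be applied to the viral load data".
- **Summary measure, per participant and on that scale:** "the median log viral load will be estimated for each participant prior to treatment and at time points post treatment".
- **Test:** the sentence that opens "Generalized estimating equations (GEE) will be used to assess change over time with" applies GEE to this summary.
- **Blood samples:** Section 2.4.4 states "we would like to obtain 2 samples pre-treatment and 8 samples on treatment". Appendix II schedules "2 total blood samples during weeks -4 to 0" and, on treatment, "Each visit (every 2 weeks) after starting HD-NFV (8 samples total").
- **Swabs:** Section 8.2.8.1 and Appendix II plan 14 before treatment, then two a week for seven weeks on high dose, also 14.
- **Expected viremia:** Section 2.4.4 describes it as intermittent, "present on median of 20% of days in endemic KS and on 67% of days in HIV-associated KS".

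Section 10.1 does not say what value an undetectable result takes on the log scale. It also does not say whether the on-treatment samples form one median or stay as separate time points. Section 2.4.4 mentions a Poisson mixed effects model when it justifies the timing of the blood samples. Section 10.1 does not carry that model forward.

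**The concern.** When most samples are undetectable, a participant's median depends heavily on how many samples go into it. The median of 2 is their mean, so one positive sample lifts it off the floor. The median of 8 leaves the floor only when at least 4 samples are positive. Comparing medians built from different numbers of samples can therefore show a change when the underlying distribution has not moved.

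The trial has no control arm that would expose such a shift. Section 2.4.4 calls the effect on KSHV replication an important outcome, KSHV copy number in saliva is a secondary objective (Section 1.2.4), and Section 2.3 includes HIV-negative participants so that a direct antiviral effect can be examined. If their viremia resembles the endemic figure, the blood artefact would be largest in that group.

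**Working it through.** The plan states no power, effect size or standard deviation for this comparison, so there is no figure of its own to reproduce.

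**Inputs from the documents.** Blood 2 before and up to 8 on treatment; swabs 14 before and 14 on treatment (2 per week); viremia on 20% or 67% of days; 18 HIV-positive and 18 HIV-negative participants (Section 10.2).

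**Assumptions not in the documents.** Undetectable results are set at a floor. HIV-negative participants are at 20% detection and HIV-positive at 67%. The base case has a floor of 1.7 log10, detected loads N(3.5, 1), and detection rates that vary between participants (beta, concentration 1.5 or 4). A two-sided 5% paired t-test stands in for the GEE.

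**1. Blood, on-treatment samples pooled: chance that the median exceeds the floor.** The median of 8 averages the 4th and 5th ordered values, so it exceeds the floor when at least 4 samples are detected.

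| Detection | 2 samples | 8 samples |
|---|---|---|
| 20% | 1 - 0.8² = 36.0% | P(Bin(8, 0.2) ≥ 4) = 5.6% |
| 67% | 1 - 0.33² = 89.1% | P(Bin(8, 0.67) ≥ 4) = 91.5% |

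At 20% the two summaries differ sharply. At 67% they exceed the floor about equally often, so any shift depends on the shape of the load distribution.

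**2. Blood, pooled, simulated with no drug effect (base case, 36 participants, 8 on-treatment samples each).**

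| Cohort | False rejection |
|---|---|
| All 36 at 20% | about 30-60% |
| 18 at 20%, 18 at 67% | about 17-30% |
| All 36 at 67% | about 15% |
| Per-sample means instead of medians | about 4-8% |

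Three other load distributions, with one common detection rate per group, give a significant false fall in 50-66% of trials (18 HIV-negative alone), 3-19% (18 HIV-positive alone) and 21-42% (18/18 mix). The mix gives 16-24% once rates vary between participants. The mean false change is -0.10 to -0.36 log10 at 20% and -0.18 to 0.00 at 67%.

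Eight samples is a maximum. If 40% of participants gave only 2 on-treatment samples (an assumption), the base-case rate for the 18/18 mix drops to about 10-12%.

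**3. Blood, each visit its own time point.** A visit has one sample x, which is its own median. The baseline median is (x₁ + x₂)/2. With no drug effect both have expectation E(x), so the expected change is 0.00.

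**4. Swabs, pooled.** 14 against 14 gives no bias.

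**5. Swabs, each week its own time point.** The weekly median of 2 is a mean, with expectation E(x). The baseline median of 14 exceeds the floor only if at least 7 swabs are positive. At 20% detection, borrowed from blood for illustration, P(Bin(14, 0.2) ≥ 7) = 1.2%. The baseline therefore usually lies below E(x), and a false rise follows. The base case gives +0.18 to +0.26 log10 at 20% and +0.16 to +0.19 at 67%. The other load distributions give about +0.08 to +0.23 with rates varying between participants, and -0.05 to +0.39 with a common rate.

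**The case against.** The strongest reply is that the plan never specifies a pooled on-treatment median. It refers to time points in the plural and to change over time. With one blood tube per visit, that reading gives no bias in blood. This stands. A reader might infer that the planned blood analysis will show a fall with no drug effect; the text does not support that as an unconditional statement. The same reading does not rescue the summary, though, because the same sentence governs the swabs. There it sets a 14-swab median against weekly 2-swab medians.

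A second reply is that the floor is itself an assumption: if quantity were summarised among positive samples only, the artefact would take another form or not arise. That also stands. A log transform still needs some rule for undetectable results, and none is given.

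Third, a rejection rate computed with every participant at 20% does not describe this trial, which plans an 18/18 mix and in which not everyone will give 8 samples. This is right, and the mixed-cohort range is the relevant one. The 20% figure is also for endemic KS, so applying it to all HIV-negative participants is an assumption.

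A reader might also infer that the median loses a calculable amount of power in saliva. The documents give no per-swab detection rate for saliva; the 20% and 67% refer to blood. No power figure can be supported.

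Finally, the analysis is exploratory, with no decision rule, and Section 10.1 also provides McNemar's test and a binomial GEE for detection. Those limit the consequence, but they do not address the quantity of virus.

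**Conclusion.** The point holds in a conditional form. Neither reading of the stated median is sound for both sources: pooling biases blood towards a fall, and time-by-time analysis generally biases saliva towards a rise. Blood by visit and swabs pooled 14 against 14 are each unbiased, but the plan does not specify that split.

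Under pooling with non-detects at a floor, false rejection in blood is about 17-30% for the planned mix (up to 42% in one case with a common detection rate per group), lower if many participants have fewer than 8 samples, and about 15% or less at 67% detection in the base case. The binomial contrast of 36.0% against 5.6% depends only on the 20% rate, independence between samples and the floor. The rejection rates and log10 shifts also depend on the assumed load distributions, and the saliva shifts on assumed detection rates.

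The primary response endpoint is unaffected. The change is still worth making, because the effect on KSHV replication is described as an important outcome and the remedy is inexpensive.

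**What to change.** In Section 10.1, replace the per-participant median with a sample-level analysis, for each virus and source:

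- Use log10 copies from every sample as the outcome, in a GEE or mixed model with participant clustering and a period effect (before treatment against on high dose).
- State the non-detect rule in advance: either treat undetectable results as left-censored in a mixed model, or set them to one named value below the assay limit.
- Report quantity among positive samples descriptively, beside the detection analyses already planned.
- Reconcile this with the Poisson mixed effects model mentioned in Section 2.4.4.

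The cost is SAP wording and modest extra modelling on the same data, with no added samples or visits. The downside is some dependence on the chosen non-detect value or on the censoring assumption, which a sensitivity analysis with a second value would show.
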